7.0 Study Agent Administration

Study participation will be discontinued if subject experience any of the side effects listed in section 8.0

A participant may always be removed from study participation whenever he/she wishes

8.0 Assessment of Efficacy and Safety

Side effects and toxicities to be monitored:

1. Anaphylactic reaction: symptoms include flushing, itching, swelling, difficulty breathing, and fainting.
2. Nerve Weakness
3. Infection
4. Fever
5. Swelling
6. Abscess formation
7. Dizziness
8. Visual Disturbances
9. Headache
10. Nausea
11. Seizure
12. Diarrhea
13. Abdominal pain
14. Arrhythmia (abnormal heart rhythm)

Because only 2-4 mL of 2% lidocaine with epinephrine will be used there will be no longterm follow-up for these subjects.

The principal investigator is the individual responsible for monitoring and reporting the occurrence of adverse events throughout the study. Subjects will be monitored throughout the study. Subjects will be taken off the study participation if they experience any side effects. USC orthopaedic staff will also monitor for any un-anticipated events. Anticipated adverse events are discussed in the Informed Consent Form for this study.

The research team will follow the IRB Adverse Even Policy on mandatory reporting of Serious Adverse Events (SAEs), and we will also report them immediately both orally and in writing to the IRB Program Director within 24 hours of occurrence or recognition.

9.0 Clinical and Laboratory Evaluations

Medical History Assessment Questions:

1. Are you over the age of 18?
2. Are you pregnant or think you could possibly be pregnant?
3. Have you used antibiotics in the last month?

Back Examination:

1. Inspection of the back of any lesions, rash, acne, or deformities.

10.0 Criteria for Evaluation and Endpoint Definitions

All eligible subjects who meet inclusion criteria will be included in the analysis.

The primary outcome will be positive growth of *P. acnes* on culture. Secondary outcome will be subtyping based on hemolysis. The USC Microbiology lab assess the samples and will be blinded to treatment condition. They will only receive the participant ID and corresponding treatment number.

11.0 Data Collection and Monitoring

Protections against risks:

All key personnel have completed courses on protection of human subjects.

Protections against biomedical risks:

Only qualified trained orthopaedic surgeons will be performing the biopsies using sterile technique.

Confidentiality:

To minimize this risk, only the investigators will have access to all data containing personal information. All data will be locked in the PI's office and/or lab. To preserve confidentiality, immediately after enrollment the subjects will be assigned a code by which each research subject will be identified for further analysis.

Data management:

All the study data will be collected by the research team and recorded on data collection form, found in section 16.0. Immediately after enrollment each subject will be assigned a code by which each research subjects will be identified for further analysis to avoid identification by non-qualified individuals.

12.0 Statistical Considerations

Statistical Analysis:

Primary outcomes will be treatment comparisons on the percentage of subjects with positive cultures for *P. acnes*. Primary outcomes will be analyzed using generalized estimating equations to account for the within-subject correlated outcomes, as all 4 interventions will be evaluated on each subject. Given the dichotomous outcome (presence/absence of *P. acnes*), the analysis will use a logistic model (binomial random outcome with a logit link function). Three indicator treatment variables will be specified (e.g., clindamycin, benzoyl peroxide, clindamycin plus benzoyl peroxide; with lidocaine as the referent group). A 3df overall test of the treatment indicators will test for any differences in positivity for *P. Acnes* among the treatments; pairwise comparisons among the treatments will adjust for multiple comparisons. A two-tailed statistical test will be performed, testing at an alpha of 0.05. Analyses will also be performed based on hemolytic subtypes.

Power Analysis:

Data from previous studies were used to estimate that 70% of cultures will grow positive for *P. acnes* with no therapy.⁴ For a clinically meaningful response, we would expect only 5% of cultures to grow positive for *P. acnes* following treatment. Thus, using a McNemar test for paired proportion comparison, with an alpha of 0.05 and power of 80%, we would need a minimum of 12 biopsies per treatment group to have adequate power.

Sample Size:

We will recruit a minimum of 12 total subjects to achieve adequate power. Because each patient is receiving 4 biopsies, there will be a total of 48 samples.

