1.0 Background

Great efforts are undertaken in the perioperative period to avoid infection, a major cause of morbidity and mortality. Still, infection rates can range from 0.6% to 5%, depending on the type of surgery performed.¹ Studies in the orthopaedic literature have shown that organisms usually characterized as more indolent, such as *P. acnes*, a known skin pathogen, cause surgical site infections following shoulder surgery despite proper preoperative surgical preparation.² Matsen et al. hypothesized that *P. acnes* infections do not originate from the superficial epidermis, but from the dermal layer, which may be expected as *P. acnes* is known to reside in the sebaceous glands and hair bulbs.^{2,3}

Lee et al. showed a 70% growth rate of *P. acnes* despite the application of Chloraprep prior to sampling, contradicting previous studies that found only 7% growth in the superficial layer of the skin using the same skin preparation.^{4,5} However, this study was limited as it failed to utilize a control group and only investigated one preparatory technique. Meanwhile, there remains to date no study investigating the effect of topical treatments in eradicating *P. acnes* within the dermal layer. The purpose of this study is to investigate how specific topical treatments affect growth in the dermal layer.

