2.0 Objective and Purpose

1. What is the prevalence of Propionibacterium in the dermal layer following topical treatments?
2. Does the type of topical treatment used affect the prevalence of Propionibacterium in the dermal layer?

Primary Outcome:

Positive growth of Propionibacterium acnes on bacterial culture.

Secondary Outcomes:

Positive hemolysis on brucella agar.

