6.0 Sample Size

We will recruit participants until there are 12 total subjects.

Power Analysis:

Data from previous studies were used to estimate that 70% of cultures will grow positive for *P. acnes* with no therapy.⁴ For a clinically meaningful response, we would expect only 5% of cultures to grow positive for *P. acnes* following treatment. Thus, for an alpha of 0.05 and power of 80%, we would need a minimum of 12 biopsies per treatment group to have adequate power, based on a McNemar test for paired proportion comparison.

Sample Size:

We will recruit a minimum of 12 total subjects to achieve adequate power. Because each patient is receiving 4 biopsies, there will be a total of 48 samples.

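### Objective 1 asks for the prevalence after each treatment, but Section 12.0 plans only logit comparisons: no per-site interval, and no usable estimate when a gel has 0/12 positive

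*Combined protocol and SAP*

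**What the plan says.** Section 2.0 sets two questions. The first is one of estimation: "What is the prevalence of Propionibacterium in the dermal layer following topical treatments". The second asks whether the type of treatment changes that prevalence.

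Section 12.0 addresses the second. It defines the primary outcomes as "Primary outcomes will be treatment comparisons on the percentage of subjects with positive cultures for" P. acnes. It uses generalized estimating equations with three treatment indicators, and says that "the analysis will use a logistic model (binomial random outcome with a logit link function"). On testing it says "A 3df overall test of the treatment indicators will test for any differences in positivity for" P. acnes, that "pairwise comparisons among the treatments will adjust for multiple comparisons", and "A two-tailed statistical test will be performed, testing at an alpha of 0.05".

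No section specifies an estimate with a confidence interval for any site, a difference in percentages, or what to do when a site has no positive cultures. Section 10.0 restates the outcomes and adds nothing on this.

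The power text, in Sections 6.0 and 12.0, takes 70% positive without therapy and says "For a clinically meaningful response, we would expect only 5% of cultures to grow positive for" P. acnes after treatment. The analysis text does not return to the 5%.

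**The concern.** A stated objective has no stated analysis. A prevalence from 12 biopsies is imprecise, and without a planned interval the report can give a bare percentage that looks firmer than it is.

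The gap is widest where a gel works best. A site with no positive cultures is a likely result under the plan's own assumptions, and there a logit model cannot return an effect size. The reader would then have a percentage of zero without a limit, a coefficient that is an artefact of the fitting algorithm, and a p-value that means nothing. That leaves room to read 0/12 as elimination of the organism, or a significant test as proof of a low prevalence.

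**Working it through.** **Inputs.** 12 subjects with one biopsy per treatment each (Section 6.0); 70% positive untreated and 5% treated, two-sided alpha 0.05, power 80% (Sections 6.0 and 12.0). Assumptions: all 12 subjects complete; GEE tests in Wald form with robust standard errors, because Section 12.0 names no form; the referent is the untreated site of Section 3.0, although Section 12.0 calls it lidocaine.

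**1. The plan's own figure.** If a subject's sites are independent (the plan states no correlation), the discordant probabilities are 0.70 × 0.95 = 0.665 and 0.30 × 0.05 = 0.015. Exact two-sided McNemar power is 79.9% at n = 11 and 86% at n = 12, so 12 is reproduced. Across the possible correlations, power at 12 runs from 76.6% to 91.5%. The sample size for the paired comparison is not in dispute here.

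**2. Precision of one site's prevalence.** For 0/12:
- exact (Clopper-Pearson) upper limit: 1 − 0.025^(1/12) = 26.5%
- Wilson upper limit: 1.96² / (12 + 1.96²) = 3.84 / 15.84 = 24.2%

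Exact 95% intervals for other counts: 1/12, 0.2% to 38.5%; 2/12, 2.1% to 48.4%; 3/12, 5.5% to 57.2%; 4/12, 9.9% to 65.1%.

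**3. How often 0/12 arises.** The probability is (1 − p)^12: 0.95^12 = 54% at a true 5%, 0.90^12 = 28% at 10%, and 0.85^12 = 14% at 15%. If all three gels are at 5%, at least one gives 0/12 with probability 1 − (1 − 0.54)^3 = 90% if gels are independent within subjects, and 54% if they agree completely.

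**4. What the planned model does then.** The gel coefficient is logit(gel) − logit(control), and logit(0) is minus infinity. An illustrative GEE fit (control 8/12, gels 0/12, 4/12 and 2/12) stopped at −25.3 with an independence working correlation and −32.3 with an exchangeable one. The robust standard error was about 0.68 in both, so the Wald ratio is −25.3 / 0.68, about −37, and p is numerically zero. The software reported convergence.

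The same happens with control 2/12 against gel 0/12: p is again effectively zero. The exact McNemar test on those two discordant pairs gives 2 × 0.5² = 0.50. The Wald p-value therefore carries no evidence.

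**5. What stays usable.** Take control 8/12 and gel 0/12, so 8 pairs are discordant, all one way. The difference is 8/12 = 66.7 points. Tango's score interval comes from two equations in the difference D:
- Lower limit (D below 0.5): (8 − 12D)² = 3.84 × 12 × (2/3 − D)(1 + D). This reduces to 96 − 144D = 46.1 + 46.1D, so D = 49.9 / 190.1 = 26.3 points.
- Upper limit (D above 0.5): the score equation becomes Wilson's for 8/12, whose upper limit is 100% minus the Wilson lower limit for 4/12, or 100 − 13.8 = 86.2 points.

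The interval, 26 to 86 points, is wide but finite and readable.

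**The case against.** The strongest reply is that this is a reporting omission. Section 12.0 does name percentages, the data sheet in Section 16.0 records culture result by biopsy group, and raw percentages would very probably be reported. With one indicator per treatment, the fitted model returns the observed site percentages, and intervals follow from the same fit. The plan never says that an odds ratio will be its headline.

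Much of that stands. What is missing is the planned estimate with its uncertainty. The model-based route also fails at 0/12 (or 12/12), and 0/12 is no rare corner at the assumed 5%.

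Three stronger readings are tempting, and the documents do not support them:
- *That the trial sets out to show 5% or less and cannot.* The 5% appears only in the power text, as the rate expected under treatment. It is linked there to a clinically meaningful response, but it is not a success threshold. Results of 0/12 and 1/12 are both compatible with it.
- *That the plan will call any difference with p below 0.05 clinically meaningful.* The plan has an overall test and multiplicity-adjusted pairwise tests, and it states no such rule.
- *That the plan will claim eradication.* The word belongs to Section 1.0, which notes "no study investigating the effect of topical treatments in eradicating" the organism in the dermis. It is not an endpoint or a planned conclusion. The misreading is a risk left open, not something stated.

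**Conclusion.** The concern holds in limited form. Objective 1 has no pre-specified estimate with an interval, and Section 12.0 gives no effect on the percentage scale, which is the scale of its own primary outcome. The upper 95% limit for 0/12 is 24% to 26% by the two methods shown. At a true 5% each gel has a 54% chance of 0/12, and the planned coefficient is then not finite.

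The interval limits rest only on n = 12 and the choice of method. The 54% rests on the plan's assumed 5%. The statement about the p-value rests on a Wald test. A score test does not need the unrestricted estimate and would not fail in this way, but the plan does not specify one. The gap should be closed before analysis; it does not undermine the design or the sample size for the paired comparison.

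**What to change.** In Section 12.0:

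1. Answer Objective 1 with x/12 and an exact 95% interval for each of the four sites.
2. Report each gel-control effect as a paired difference in percentage positive with a 95% score interval (Tango), beside the multiplicity-adjusted test. State which test is used when a site is 0/12 or 12/12, since the Wald form cannot be. A score test or the exact McNemar test, with the chosen adjustment, would serve.
3. State that a significant test shows a reduction against control only, and that any statement about how low the prevalence is rests on the upper confidence limit.

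**Cost.** A few lines of text and code, with no extra subjects or biopsies. The reported claim will look less favourable, because the intervals are wide. If exact McNemar with Bonferroni adjustment is chosen, power at n = 12 under the plan's rates and independence is 71% for three comparisons and 55% for six. The choice of test and number of comparisons should be made with that in view.

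### At the planned 5% treated rate a 0/12 arm is likely; the logit GEE then has no finite estimate for it, and the plan fixes neither the test nor a rule for that case

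*Combined protocol and SAP*

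**What the plan says.** Section 12.0 (Statistical Analysis) sets the primary analysis: "Primary outcomes will be analyzed using generalized estimating equations to account for the within-subject correlated outcomes". The model is binomial with a logit link and three treatment indicators, "with lidocaine as the referent group". "A 3df overall test of the treatment indicators" addresses any difference, and "pairwise comparisons among the treatments will adjust for multiple comparisons". Testing is two-sided at 0.05.

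The section does not say whether the tests are Wald or score. It names no variance estimator, working correlation or multiplicity method, and it does not say what happens if an arm has no positive cultures. No other section supplies these.

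Sections 6.0 and 12.0 assume 70% positive without therapy. After treatment, "we would expect only 5% of cultures to grow positive for" the organism. Twelve subjects follow, "based on a McNemar test for paired proportion comparison". Objective 2 in Section 2.0 asks: "Does the type of topical treatment used affect the prevalence of Propionibacterium in the dermal layer".

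**The concern.** The better the treatments work, the more likely the primary model is to break down. At 5%, the expected count is 12 × 0.05 = 0.6 positives per treated arm. When the count is zero, the log-odds for that arm runs to minus infinity. Software stops at an arbitrary large value and may still report convergence. What the Wald test then says depends on a variance option that the plan leaves open.

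Two analysts who both follow Section 12.0 could therefore reach opposite conclusions from the same 48 cultures. One could report that two equally effective treatments differ, which is the question in Objective 2. The other could report that a treatment that cleared every culture is no different from control.

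The same sentence has a labelling slip. Lidocaine is injected at every biopsy site (Section 3.0), so it cannot be the referent. The comparator is the untreated quadrant, listed as Control in Section 16.0.

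**Working it through.** **Inputs from the plan:** control 70%, treated 5% (one figure for all treatments), 12 subjects each giving one biopsy per condition, two-sided 0.05, McNemar sizing at 80% power.

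**Assumptions added here:** all three treated arms share one rate; latent-normal within-subject correlation is 0 to 0.6; simulated Wald pairs are tested at 0.05/6, because no adjustment method is named.

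**1. The plan's own figure.** Under within-subject independence the discordant probabilities are 0.70 × 0.95 = 0.665 and 0.30 × 0.05 = 0.015. Exact two-sided McNemar power is 0.799 at n = 11 and 0.861 at n = 12, so the planned 12 is reproduced. It applies to one unadjusted comparison.

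**2. How often an arm is 0/12.**

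| Treated rate | One given arm | At least one of three, independent | Same, correlation 0-0.6 |
|---|---|---|---|
| 5% | 0.95^12 = 0.540 | 1 − 0.460^3 = 0.903 | 83-90% |
| 10% | 0.90^12 = 0.282 | 1 − 0.718^3 = 0.631 | 55-63% |
| 20% | 0.80^12 = 0.069 | 1 − 0.931^3 = 0.192 | 17-19% |

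If any one arm is truly at 5%, the chance of at least one 0/12 arm cannot fall below 54%.

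**3. Why the variance estimator decides the answer.** Take an independence working correlation and an arm with fitted probability m.
- Model-based variance of its log-odds: 1/[12m(1−m)]. This goes to infinity as m goes to 0.
- Robust variance: Σ(y−m)²/[12m(1−m)]². With every y = 0 this is 12m²/[144m²(1−m)²], which goes to 1/12 = 0.083.

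So as the coefficient diverges, the robust SE stays small and the model-based SE explodes.

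**4. Example: control 8/12, treated 1/12, 0/12, 0/12** (control positive in subjects 1-8, first treated arm positive in subject 1).
- Log-odds variances: control 1/(12 × 8/12 × 4/12) = 0.375; the 1/12 arm 1/(12 × 1/12 × 11/12) = 1.091.
- The 0/12 coefficient stopped at about −26 (independence) or −30 (exchangeable).
- Robust SE, 0/12 against control: √(0.375 + 0.083) = 0.677, so |z| is 39 to 45. For 1/12 against 0/12: √(1.091 + 0.083) = 1.084, so |z| is 21 to 25.
- Model-based SE for the 0/12 coefficient: above 100,000, so z is about 0 for both contrasts.
- Model-based 3-df Wald: the zero arms contribute nothing. What remains is [ln(1/11) − ln 2]²/(0.375 + 1.091) = 9.55/1.466 = 6.5, p = 0.089. With exchangeable correlation it is 6.9, p = 0.074.
- Paired tests, 0/12 against control (8 discordant pairs, all one way): exact 2 × 0.5^8 = 0.0078, mid-p 0.0039. For 1/12 against 0/12 (one discordant pair): exact 1.0, mid-p 0.5.
- Permutation Cochran's Q: 6 × 4^7 = 98,304 arrangements, 12 as extreme, p = 0.00012.

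| Comparison | Robust Wald p | Model-based Wald p | Exact or permutation p |
|---|---|---|---|
| Overall | effectively 0 | 0.07-0.09 | 0.0001 |
| 0/12 vs control | effectively 0 | about 1.0 | 0.008 |
| 1/12 vs 0/12 | effectively 0 | 1.0 | 1.0 |

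**5. How often this matters at 70/5/5/5** (20,000 simulated trials per scenario; 6,000 for permutation Q).
- Robust Wald shows at least one false active-vs-active difference in 59-75% of trials.
- Model-based Wald has 22-24% power per treatment-vs-control pair. Mid-p McNemar with Holm over six pairs has 74-78%.
- Model-based 3-df Wald rejects in 52-53%. Permutation Q rejects in 98-99.7%.

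Fitted exchangeable GEE models (250 runs per correlation) gave similar results: false active differences in 56-75%, model-based control-pair power 18-31%, and model-based 3-df power 47-54%.

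**The case against.** The 5% rate is a sizing target for a meaningful response, not a forecast that all three treatments reach it, and the problem shrinks quickly at higher rates. That is true, and the table shows it. Still, it is the only treated rate the plan gives.

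The correlation range is also a choice. Four sites on one back could be more alike: at latent correlation 0.8 and 0.95, at least one 0/12 arm occurs in 76% and 66% of trials. Trials with some but not all treated arms at zero, which produce the false active-vs-active signal, fall to 45% and 25%. These are lower but not negligible.

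Part of the model-based power deficit comes from small n and a strict threshold. Even when the treated arm is not 0/12, power at 0.05/6 is only 47-50%. That is fair, but mid-p McNemar at the same flat threshold has 72-78%.

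A careful analyst would notice a diverged fit, and a GEE score test would also satisfy Section 12.0. Both points stand: the analysis is unspecified, not impossible. Model-based Wald does not always miss the overall effect either; with counts 8, 1, 1, 0 it gave p = 0.012-0.016. But noticing a diverged fit after unblinding leaves the choice of test to be made with the results in view.

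Finally, exact McNemar would serve instead of mid-p. That is a legitimate preference, at a cost in power.

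**Conclusion.** The concern holds and should be fixed before analysis. Under the plan's own sizing assumption a given treated arm is more likely than not to be 0/12. Wald results involving that arm then reflect the variance option rather than the data: the robust version separates equally effective treatments in most trials, and the model-based version misses most real differences from control.

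The frequencies rest on 70% against a common 5% and on correlation 0-0.6. The absence of a finite estimate for a 0/12 arm does not depend on those assumptions. Contrasts among arms with finite estimates, and the observed percentages, are unaffected.

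**What to change.** 1. **Overall test:** a within-subject permutation test of Cochran's Q (size 2.5-4.6% under global nulls at 30%, 50% and 70%). A GEE score test is workable if its df equal the rank of its covariance, which is singular in 60-73% of trials at 70/5/5/5. Its power is 90-92% there, but only 47-49% against 73-89% for permutation Q at 70/20/20/20.
2. **Pairwise tests:** mid-p McNemar for all six pairs, Holm-adjusted over the six, not conditional on the overall test and with no gate on the active-vs-active pairs. Familywise error is at most 2.3% under those global nulls.
3. **Estimates:** paired risk differences with Tango score intervals. They stay finite when both arms are 0/12: 0 ± 3.84/(12 + 3.84), or ± 24 percentage points.
4. **GEE odds ratios:** supportive only, with stated working correlation and variance estimator, reported as not estimable for a 0/12 or 12/12 arm. A small-sample sandwich correction does not cure the problem: p stays effectively 0 in the example.
5. **Referent:** replace lidocaine with the untreated control quadrant.
6. **Power statement:** say that the 80% applies to one unadjusted comparison.

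**Cost.** SAP wording, short code and a power loss to declare. At 70% against 5% with n = 12, one unadjusted pair has 86% (exact) or 93% (mid-p) at zero correlation. After Holm over six, mid-p gives 74-78% per control pair and 58-69% for all three; exact McNemar gives 56-58% and 39-46%. For 80% after adjustment, 13 subjects give 81-87% per control pair and 15 give about 80-92% for all three.

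Power between active arms is limited. At least one difference is found in 83-85% of trials at 70/70/5/5, but in 9-11% at 70/40/20/5 and under 1% at 70/20/20/5. The SAP should say that a non-significant active-vs-active result is not evidence of equal efficacy.

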3.0 Study Design

Twelve healthy volunteers who are over the age of 18 will be consented to participate in our study. Those individuals with active acne or those who received a course of antibiotics in the last month will be excluded. The subject's upper back will be sectioned into quadrants above the scapular spine, which will be each assigned a different topical treatment: clindamycin alone, benzoyl peroxide alone, clindamycin plus benzoyl peroxide, and a control, with no topical application. Each application will be applied twice daily for 3 consecutive days. Randomization will be performed using a random number generator to draw numbers 1-4 in order to designate a topical treatment to each quadrant. Quadrants will be labeled with surgical markers to ensure the correct treatment is applied. Research subject will be trained on application using a mirror with the research staff during recruitment.

A 3-mm dermal punch biopsy specimen will be obtained at each site using a commercially available kit after prepping with isopropyl alcohol and sterile injection of local anesthesia with 2% lidocaine with epinephrine. The biopsy sites will be covered with sterile gauze and allowed to heal without closure. Unfortunately, due to procedural limitations, the dermal layer of the skin cannot be accessed without penetrating the epidermis. Thus even separating the dermis from the epidermis is not helpful because the dermis will have been contaminated from potential pathogens from the epidermis during the biopsy procedure.

A total of four punch biopsies will be obtained from the subject's back; one for each of type of topical treatment and the control. The four punch biopsy specimens will then be cultured for *P. acnes*, with serotyping, and held for 21 days to assess for growth. Assessment of growth will be made the USC Microbiology Lab, who will be blinded to the treatment condition.

Pipettes will be used to inoculate the fluid onto the following media: blood agar, chocolate agar, brucella agar, and brain heart infusion broth. This same culture technique was used by Lee et al, in their published study investigating *P. acnes* levels in the dermis of the skin.⁴ In order to determine hemolytic subtype, the samples will also be tested on Brucella Blood agar, as described by Wright et al.⁶

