16.0 Data Collection Sheet

Pt Code	Age	Sex	Biopsy group (Control vs. Clindamycin vs. Benzoyl Peroxide vs. Clindamycin and Benzoyl Peroxide)	Positive Culture	Hemolytic Subtype	Adverse Events?

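### Does naming lidocaine as the referent group mis-specify the primary comparison?

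*Combined protocol and SAP*

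**What the plan says.** Section 12.0 (Statistical Considerations) gives the primary method: "Primary outcomes will be analyzed using generalized estimating equations to account for the within-subject correlated outcomes". On coding it says "Three indicator treatment variables will be specified (e.g., clindamycin, benzoyl peroxide, clindamycin plus benzoyl peroxide", and it closes the same parenthesis "with lidocaine as the referent group". An overall 3 df test and multiplicity-adjusted pairwise comparisons follow.

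Section 3.0 (Study Design) lists the four quadrant assignments: "clindamycin alone, benzoyl peroxide alone, clindamycin plus benzoyl peroxide, and a control, with no topical application". Its only mention of lidocaine concerns the biopsy procedure. "A 3-mm dermal punch biopsy specimen will be obtained at each site", and this is done "after prepping with isopropyl alcohol and sterile injection of local anesthesia with 2% lidocaine with epinephrine".

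Section 16.0 (Data Collection Sheet) codes the group variable as "Biopsy group (Control vs. Clindamycin vs. Benzoyl Peroxide vs. Clindamycin and Benzoyl Peroxide". The power paragraphs in Sections 6.0 and 12.0 set 70% culture positivity without treatment against 5% with it.

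**The concern.** The referent gives each model odds ratio its meaning. Section 12.0 names as referent a substance that every site receives and that no group is defined by. Read literally, the sentence governing all three primary coefficients, and the three control comparisons among the six possible pairs, points to a group that does not exist.

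The stake would be interpretation. An effect reported as versus lidocaine suggests an active or sham comparator. The design gives an effect versus no topical application, with alcohol preparation and lidocaine common to both sides. If the wrong name could also lead an analyst to a different model, the estimates themselves would be at risk.

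**Working it through.** **1. Which group is the referent?** The inputs are the four groups (Sections 3.0 and 16.0), the three named indicators (Section 12.0), 12 subjects and 4 sites each (Section 6.0).

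| Group | Clindamycin indicator | Benzoyl peroxide indicator | Combination indicator | Samples |
|---|---|---|---|---|
| Control | 0 | 0 | 0 | 12 |
| Clindamycin | 1 | 0 | 0 | 12 |
| Benzoyl peroxide | 0 | 1 | 0 | 12 |
| Combination | 0 | 0 | 1 | 12 |

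The total is 12 × 4 = 48 samples. The three indicators account for 3 × 12 = 36, and the other 48 − 36 = 12 are the control samples. The intercept is the control log odds, and each coefficient is a topical treatment against control. Putting the correct name on the referent leaves this coding as it is, so the estimates are the same before and after.

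**2. Would another referent alter the tests?** A logistic GEE was fitted with exchangeable working correlation to illustrative data. These were invented for the check and are not trial results: 8, 5, 3 and 2 positives out of 12 in groups 0 (control), 1, 2 and 3. Each group served as referent in turn.

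| Referent | 3 df Wald | Log odds ratios of the other groups |
|---|---|---|
| 0 (control) | 19.06 | group 1: −1.030; group 2: −1.792; group 3: −2.303 |
| 1 | 19.06 | group 0: 1.030; group 2: −0.762; group 3: −1.273 |
| 2 | 19.06 | group 0: 1.792; group 1: 0.762; group 3: −0.511 |
| 3 | 19.06 | group 0: 2.303; group 1: 1.273; group 2: 0.511 |

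The overall test does not depend on the referent. Every pairwise contrast can be recovered by subtraction: group 2 against group 1 is −1.792 − (−1.030) = −0.762, which matches the second row. All pairs are compared under the plan anyway.

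**3. Does the sample size depend on the label?** The plan's figure is 12 per group (McNemar, 70% against 5%, alpha 0.05, power 80%). The within-pair correlation is not stated, so independence is assumed first:

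- p10 = 0.70 × 0.95 = 0.665 and p01 = 0.30 × 0.05 = 0.015. The discordant share is 0.665 + 0.015 = 0.68, and the difference is 0.65.
- Exact conditional McNemar test, two-sided: power is 79.9% at 11 and 86.1% at 12, so the smallest adequate number is 12.
- Asymptotic formula: n = (1.96 × √0.68 + 0.842 × √(0.68 − 0.65²))² / 0.65² = 9.88, rounded up to 10.
- From maximum positive correlation (discordant share 0.65) to maximum negative (0.75), the exact answer runs from 11 to 13.

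The plan's 12 therefore reproduces with the exact test under independence. Its comparator input is already the untreated rate, so the word lidocaine enters nowhere.

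**The case for a change.** The best case for a change is that the misreading is not far-fetched. Section 4.0 lists four products, three gels and lidocaine with epinephrine, and Section 12.0 then speaks of four interventions evaluated on each subject. Taken together, these could suggest a lidocaine arm. No section says that lidocaine is shorthand for the control quadrant. A pre-specified primary analysis should not name a group that does not exist, and the correction would cost one sentence.

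The factual part stands: the word is wrong, and the documents do not define it as shorthand. The consequence does not follow. Section 3.0 describes the fourth quadrant as "and a control, with no topical application", the data sheet calls it control, and the power text uses an untreated rate, so everything else in the document points the same way. The analyst works from a dataset with no lidocaine category to select. It is also true that a lidocaine indicator would be constant over all 48 samples and collinear with the intercept (rank 4 of 5 columns), but the plan proposes no such indicator. It names lidocaine only as the omitted level. Adding that alcohol and lidocaine are common to all sites would repeat Section 3.0.

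The list of indicators is introduced as an example, so another coding is open in principle. Step 2 of the working shows that this would not matter either.

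**Conclusion.** Section 12.0 misnames its reference level. This is a clerical slip, and no change to the plan follows. The three named indicators and the four recorded groups determine the model: its referent is the untreated control quadrant. Correcting the name changes 0 of 3 coefficients, 0 of 6 pairwise contrasts, neither the 3 df test nor its p-value, and not the 12 subjects. The possible harm is confined to how a results table is labelled, and the design section and the data sheet already give the right label.

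The conclusion rests on two things. One is that alcohol preparation and lidocaine are used alike at all four sites, as Section 3.0 describes. The other is that the group variable is taken from the data sheet in Section 16.0. The sample-size check also assumes a within-pair correlation that the plan does not state, but over its full range the exact result stays between 11 and 13 and does not depend on the referent's name.
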